6.2.1.8. Overall Survival

Overall survival (OS) is defined as the time from date of first dose of study treatment to the date of death due to any cause. Patients last known to be alive will be censored at date of last contact.

$$\text{OS (months)} = [\text{date of death or censoring} - \text{date of first dose of study treatment} + 1] / 30.4375$$

Kaplan-Meier estimates (product-limit estimates) will be presented by treatment group together with a summary of associated statistics including the median OS time with 2-sided 95% CIs. In particular, the OS rate at 2, 4, 6, 8, 12, 16, 18 and 24 months will be estimated with corresponding 2-sided 95% CIs. The CIs for the median will be calculated according to [Brookmeyer and Crowley](#) and the CIs for the survival function estimates at the time points defined above will be derived using the log-log transformation according to [Kalbfleisch and Prentice](#) (conftype=loglog default option in SAS Proc LIFETEST) with back transformation to a CI on the untransformed scale. The estimate of the standard error will be computed using Greenwood's formula.

Frequency (number and percentage) of patients with an event (death) and censoring reasons will be presented by treatment group. Reasons for censoring will be summarized according to the categories in Table 8 following the hierarchy shown.

Table 8. OS Censoring Reasons and Hierarchy

Hierarchy	Condition	Censoring Reason
1	No event and [withdrawal of consent date \geq date of first dose of study treatment OR End of study (EOS) = Subject refused further follow-up]	Withdrawal of consent
2	No event and [lost to follow-up in any disposition page OR data cut-off date – last contact date >104 days]	Lost to follow-up
3	No event and none of the conditions in the prior hierarchy are met	Alive

The OS time or censoring time and the reasons for censoring will also be presented in a patient listing.

Time of Follow-Up for OS

A Kaplan-Meier plot for OS follow-up duration will also be generated to assess the follow-up time in the treatment groups reversing the OS censoring and event indicators. Kaplan-Meier estimates (product-limit estimates) will be presented by treatment group together with a summary of associated statistics including the median time of follow-up for OS with 2-sided 95% CIs. In particular, the rate at 2, 4, 6, 8, 12, 16, 18 and 24 months will be estimated with corresponding 2-sided 95% CIs.

6.2.2. Pharmacokinetic Endpoints

The following pharmacokinetic analyses will be based on the PK analyses set by treatment group.

C_{trough} and C_{max} for avelumab and axitinib will be summarized descriptively (n, mean, SD, CV, median, minimum, maximum, geometric mean, its associated CV, and 95% CI) by treatment group, cycle, and day.

Dose normalized parameters (eg, $\text{CDN-}C_{\text{max}}$, $\text{CDN-}C_{\text{trough}}$) will be reported as appropriate. The trough concentrations for avelumab and axitinib will be plotted for each dose using a box whisker plot by cycle and day in order to assess the attainment of steady state.

Pharmacokinetic parameters for avelumab and axitinib will be taken from observed values or derived from concentration-time data as described in [Section 3.2.2](#).

Presentation of pharmacokinetic data will include:

- Descriptive statistics (n, mean, SD, %CV, median, minimum, maximum) of concentrations will be presented in tabular form by treatment group, dose level, cycle, day and nominal time. Additionally similar descriptive statistics will also be generated for dose-normalized avelumab and axitinib pharmacokinetic parameters.
- Linear-linear plots of mean and median concentrations by nominal time for avelumab and axitinib will be presented for PK sampling days by treatment group, cycle, and study day. Similar plots will be presented for each individual patient concentration. Patients who have undergone inpatient dose reduction or escalation will be excluded from the median concentration-time plots.
- Pharmacokinetic parameters for avelumab and axitinib will be listed and summarized by treatment group/dose level, cycle and study day using descriptive statistics (n, mean, SD, %CV, median, minimum, maximum, geometric mean and its associated %CV, and 95% CI). In addition, dose-normalized C_{max} and C_{trough} will be summarized (as described above) using data pooled across treatment groups in which different avelumab and axitinib doses were administered.

- C_{trough} and C_{max} for avelumab will be plotted for each treatment group using a box-whisker plot by cycle and day within cycle.

6.2.3. Population Pharmacokinetic Endpoints

Pharmacokinetic and pharmacodynamic data from this study may be analyzed using modeling approaches and may also be pooled with data from other studies to investigate any association between avelumab and axitinib exposure and biomarkers or significant safety/efficacy endpoints. The results of these analyses, if performed, may be reported separately from the clinical study report.

6.2.4. Biomarker Endpoints

Biomarkers will be summarized at all timepoints described below:

- Archived tumor biospecimens and de novo Tumor Biopsy: Screening and EOT.

C

Summary statistics, using descriptive statistics (mean, SD, median, Q1, Q3, minimum, and maximum), at each timepoint, ratio to screening and percent change from the value at screening/C1D1 if available (for continuous markers) will be provided by treatment group.

6.2.5. Endpoints for Immunogenicity Data of Avelumab

Blood samples for avelumab immunogenicity testing will be collected pre-dose on Cycle 1, 2, 3, 4, 6 and 8. Subsequently, testing should be performed approximately every 8 weeks. All samples should be drawn within 2 hours before start of avelumab infusion. Additional samples for anti-avelumab antibodies (and simultaneous PK draws for measurement of avelumab) will be collected at the Day 30 Follow-up visit after the end of avelumab treatment.

Samples positive for ADA will be analyzed for titer and may be analyzed for nAb. As of the finalization of this SAP, the nAb assay is not yet available, therefore the analyses of nAb data described in the following sections will only be conducted contingent upon assay and data availability at the time of reporting.

Patients will be characterized into different ADA categories based on the criteria defined in [Table 9](#).

Table 9 Patients Characterized Based on Anti-Drug Antibody Results (ADA Status)

Category	Definition	Subjects at Risk (Denominator for Incidence)
ADA never-positive	No positive ADA results at any time point; ADA-negative patients (titer < cutpoint)	Number of patients with at least one valid ADA result at any time point
ADA ever-positive	At least one positive ADA result at any time point; ADA-positive patients (titer ≥ cutpoint)	Number of patients with at least one valid ADA result at any time point
Baseline ADA positive	A positive ADA result at baseline	Number of patients with valid baseline ADA result
Treatment-boosted ADA	A positive ADA result at baseline and the titer ≥8×baseline titer at least once after treatment with avelumab	Number of patients with valid baseline ADA results and at least one valid post-baseline ADA result
Treatment-induced ADA	Patient is ADA-negative at baseline and has at least one positive post-baseline ADA result; or if patient does not have a baseline sample, the patient has at least one positive past-baseline ADA result	Number of patients with at least one valid post-baseline ADA result and without positive baseline ADA result (including missing, NR)
Transient ADA response	If patients with treatment-induced ADA have (a single positive ADA result or duration between first and last positive result <16 weeks) and ADA result at the last assessment is not positive.	Number of patients with at least one valid post-baseline ADA result and without positive baseline ADA result (including missing, NR)
Persistent ADA response	If patients with treatment-induced ADA have duration between first and last positive ADA result ≥16 weeks or a positive ADA result at the last assessment	Number of patients with at least one valid post-baseline ADA result and without positive baseline ADA result (including missing, NR)

ADA: anti-drug antibody, NR = not reportable.

Patients will be characterized into different nAb categories based on the criteria in [Table 10](#). For nAb, treatment-boosted is not applicable since no titer result is available.

Table 10 Patients Characterized Based on Neutralizing Antibody Results (nAb Status)

Category	Definition	Subjects at Risk (Denominator for Incidence)
nAb never-positive	No positive nAb results at any time point	Number of patients with at least one valid ADA result at any time point
nAb ever-positive	At least one positive nAb result at any time point	Number of patients with at least one valid ADA result at any time point
Baseline nAb positive	A positive nAb result at baseline	Number of patients with valid baseline ADA result
Treatment-induced nAb	Patient is not nAb positive at baseline and has at least one positive post-baseline nAb result; or if patient does not have a baseline sample, the patient has at least one positive past-baseline ADA result	Number of patients with at least one valid post-baseline ADA result and without positive baseline nAb result (including missing, NR)
Transient nAb response	If patients with treatment-induced nAb have (a single positive nAb result or duration between first and last positive result <16 weeks) and nAb result at the last assessment is not positive.	Number of patients with at least one ADA valid post-baseline result and without positive baseline nAb result (including missing, NR)
Persistent nAb response	If patients with treatment-induced nAb have duration between first and last positive nAb result ≥ 16 weeks or a positive nAb result at the last assessment	Number of patients with at least one valid post-baseline ADA result and without positive baseline nAb result (including missing, NR)

ADA = antidrug antibody, nAb = neutralizing antibody, NR = no result.

The number and percentage of patients in each ADA and nAb category will be summarized.

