7.3. Immunogenicity Assessment

A 3.5 mL whole blood will be collected into a SST at the designated times to provide serum for evaluation of avelumab immunogenicity. Immunogenicity blood samples will be assayed for anti-avelumab antibodies using a validated analytical method. All of the samples that are positive for ADA may also undergo characterization for neutralizing antibodies. ADA sample at 30 day follow up is collected at 30 days after end of treatment of avelumab regardless of continuation of axitinib therapy. Additional details regarding the collection, processing, storage, and shipping of the blood samples will be provided in the Study Manual.

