6.2.5.3. Analysis of PK, Safety and Efficacy by Immunogenicity Status

The following ADA and nAb status will be used for the analyses described below.

ADA

- ADA ever-positive versus ADA never-positive;
- ADA: treatment-induced ADA versus ADA never-positive or baseline ADA positive.

nAb

- nAb ever-positive versus nAb never-positive;
- nAb: treatment-induced nAb versus nAb never-positive or baseline nAb positive.

Data listings will include immunogenicity data together with relevant PK, safety and efficacy data.

PK parameters and immunogenicity status

The following analyses will include patients in both the immunogenicity analysis set and in the PK parameter analysis set. The PK endpoints pertinent to the immunogenicity analyses are C_{trough} and C_{max} .

Blood samples for avelumab PK will be collected as outlined in the “Schedule for Pharmacokinetic Sample Collection” table of the Schedule of Assessments section of the protocol.

C_{trough} and C_{max} will be summarized descriptively (n, mean, SD, CV, median, minimum, maximum, geometric mean, its associated CV, and 95% CI) by nominal time and ADA status. Linear-linear plots of mean and median for C_{trough} and C_{max} over nominal time and by ADA status will be presented.

Among patients with treatment-induced ADA, analyses will be conducted to assess whether C_{trough} and C_{max} have any changes before and after the first positive ADA assessment. To be included in this analysis, patients must have the same PK parameter available both before and after the first positive ADA assessment. Relative PK day will be calculated as:

$$(\text{PK assessment nominal day}) - (\text{first positive ADA assessment nominal day}).$$

Nominal day is the protocol scheduled timing for an assessment. For example, if C_{trough} is collected on Day 1 of Cycle 2 and the first positive ADA result is observed on Day 1 of Cycle 3, then the relative PK day for this C_{trough} is -14. Linear-linear plots of mean and median for C_{trough} and C_{max} over relative PK day will be presented.

As data permit, the analyses described above will be repeated for nAb.

Safety and immunogenicity status

The following analyses will include patients in the immunogenicity analysis set.

The frequency (number and percentage) of patients with each of the following will be presented by ADA status.

- TEAEs, by SOC and PT;
- TEAEs leading to dose reduction of avelumab, by SOC and PT;

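### If nAb testing is incomplete, SAP Table 10 counts ADA-positive patients with no valid nAb result as nAb never-positive, so nAb incidence can be understated and the comparator group mixed

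*SAP*

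**What the plan says.** Anti-drug antibodies to avelumab, including neutralizing antibodies, are a secondary endpoint (Protocol Section 2; SAP 3.2.3). Protocol 9.3.1.2 promises the percentage of patients positive for each.

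- **Testing is optional.** Protocol 7.3: "All of the samples that are positive for ADA may also undergo characterization for neutralizing antibodies". SAP 6.2.5: "Samples positive for ADA will be analyzed for titer and may be analyzed for nAb".
- **The assay did not yet exist for this study.** SAP 6.2.5: "As of the finalization of this SAP, the nAb assay is not yet available". The nAb analyses "will only be conducted contingent upon assay and data availability at the time of reporting".
- **Definition.** Table 10 defines nAb never-positive as "No positive nAb results at any time point".
- **Denominator.** For never-positive and ever-positive nAb it is "Number of patients with at least one valid ADA result at any time point". The baseline-positive row likewise uses patients with a valid baseline ADA result.
- **Use.** SAP 6.2.5.3 compares "nAb ever-positive versus nAb never-positive" and "nAb: treatment-induced nAb versus nAb never-positive or baseline nAb positive". The PK and safety analyses by nAb status are to be done as far as the data allow.

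**The concern.** nAb testing is tiered: only ADA-positive samples go forward to the nAb assay. Counting ADA-negative patients as nAb-negative is therefore normal. The difficulty lies with ADA-positive patients who have no valid nAb result. They have no positive nAb result, so they meet the never-positive definition, and their valid ADA result keeps them in the denominator. In effect, missing is set to negative in the only patients in whom nAb could be found.

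Two outputs are affected. The ever-positive and baseline-positive percentages become lower bounds but are shown as estimates. The never-positive comparator for PK and safety may contain patients who are truly nAb-positive, which would pull the two groups together.

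**Working it through.** **The plan's own figure.** The documents give no expected ADA rate, nAb rate or testing fraction. The only design calculation (SAP 5.1.1) is the chance of seeing at least one AE in 20 patients at a true incidence of 10%: 1 − 0.9^20 = 0.878, which rounds to the stated 88%. It is unrelated to nAb and serves here only to supply the planned size of 20.

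**Classification under Table 10 as written**

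| Patient | Positive nAb result? | Valid ADA result? | Table 10 class |
|---|---|---|---|
| ADA never-positive | No | Yes | Never-positive (appropriate) |
| ADA-positive, nAb tested negative | No | Yes | Never-positive (appropriate) |
| ADA-positive, no valid nAb result | No | Yes | Never-positive (status unknown) |
| ADA-positive, nAb tested positive | Yes | Yes | Ever-positive |

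**Size.** Let N be patients with a valid ADA result, x those with a positive nAb result, and u ADA-positive patients with no valid nAb result.

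- Reported ever-positive incidence: x/N.
- Possible range among these N patients: x/N to (x+u)/N, a width of u/N. At N = 20, each undetermined patient adds 1/20 = 5 percentage points.
- Share of the never-positive group with unknown status: u/(N−x).

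Illustrations, taking N = 20 (every patient has a valid ADA result) and assumed values for the rest:

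| ADA-positive | u | x | Reported x/N | Upper bound (x+u)/N | Unknown share u/(N−x) |
|---|---|---|---|---|---|
| 4 | 0 | 1 | 1/20 = 5.0% | 1/20 = 5.0% | 0/19 = 0% |
| 4 | 2 | 1 | 1/20 = 5.0% | 3/20 = 15.0% | 2/19 = 10.5% |
| 6 | 3 | 1 | 1/20 = 5.0% | 4/20 = 20.0% | 3/19 = 15.8% |
| 4 | 4 | 0 | 0/20 = 0% | 4/20 = 20.0% | 4/20 = 20.0% |

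**Effect on the comparison.** Suppose all u undetermined patients are truly positive and resemble the tested positives. The expected difference between the groups then shrinks by the factor 1 − u/(N−x). In the second illustration that is 1 − 2/19, a loss of 10.5%. This is the most the mixing can do under that assumption; if none is truly positive, the loss is zero.

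**The row that errs the other way.** The treatment-induced nAb row has a second clause for patients without a baseline sample. It is met by a positive post-baseline ADA result, with no nAb result needed, so this row can be overstated. Such a patient, if untested for nAb, is both treatment-induced and never-positive, and so falls on both sides of the second comparison in SAP 6.2.5.3. SAP 6.2.5.1 also includes treatment-induced patients in time to nAb response, which is dated from a first positive nAb result that this patient does not have.

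**The case against.** The strongest reply is that nothing in the documents plans selective testing. The Protocol 7.3 sentence can be read as a single decision covering all ADA-positive samples, and batch testing of everything once an assay exists is plausible. The SAP makes the nAb analyses depend on data as well as assay availability, and the by-nAb comparisons on what the data permit. SAP 5.2.3 shows missing values as a separate category and SAP 5.3.1 rules out imputation, each unless otherwise specified. The summaries are descriptive, and sampling error is large: the exact 95% interval for 1/20 is 0.1% to 24.9%.

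Much of this stands as a limit on the claim. A reader might infer that nAb incidence will be understated, but the text supports only that it can be. A reader might also infer a downward bias throughout Table 10; the treatment-induced row shows otherwise. Nor do the documents support judging the effect by the nAb rate among ADA-positive patients, because Table 10 plans no such rate.

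The reply does not remove the gap. The availability conditions decide whether the analyses run, not how one undetermined patient is classed once they do. Table 10 itself foresees missing or unreported baseline nAb results in three of its denominators. It offers no missing category, and its specific definition can be taken as the exception that the general rules allow. Sampling error is a separate matter: if the true count were 3/20 rather than 1/20, the exact interval would be 3.2% to 37.9%.

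**Conclusion.** The point holds in conditional form. As written, Table 10 classes an ADA-positive patient with no valid nAb result as never-positive and keeps that patient in the denominator. If the nAb analyses are run with u such patients, the ever-positive figure is a lower bound on a range of width u/N, which is 5 percentage points per patient at N = 20. Baseline-positive incidence can be understated in the same way, and a share u/(N−x) of the never-positive comparator has unknown status. Actual bias further requires that at least one of these patients is truly positive; with complete testing it is zero. The likely size cannot be derived from the documents.

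The treatment-induced row is a separate wording fault with the opposite direction. The consequences are confined to a descriptive secondary endpoint in about 20 patients. The primary endpoint and the analyses by ADA status are untouched. The change is worth making because the stated rule misclassifies and correcting it costs little.

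**What to change.** In SAP Table 10 and 6.2.5.3:

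1. Define nAb never-positive as ADA never-positive, or ADA-positive with at least one valid nAb result and none positive. A valid negative on every ADA-positive sample need not be required; one valid result matches the patient-level convention of Table 9.
2. Add a category for ADA-positive patients whose nAb status is not determined, and leave it out of both groups in the nAb comparisons.
3. Report all-patient ever-positive incidence with the bounds x/N to (x+u)/N, and state u.
4. In the treatment-induced nAb row, let a patient without a baseline sample qualify on a positive post-baseline nAb result instead of an ADA result.

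The cost is SAP wording, one extra table category and a line of reporting, with no new samples or visits. The reported upper bound may look less favourable. The rule should be fixed before any nAb results are seen, which was still possible when the SAP was finalized because the assay was not yet available.

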6.2.5.1. Time to and Duration of ADA and nAb Response

The ADA and nAb analyses described below will include patients with treatment-induced ADA or nAb, respectively.

Time (weeks) to ADA response is defined as:

$$(\text{Date of first positive ADA result} - \text{date of first dose of avelumab} + 1)/7.$$

Time to ADA response will be summarized using simple descriptive statistics (mean, SD, median, min, max, Q1, Q3).

Duration (weeks) of ADA response is defined as:

$$(\text{Date of last positive ADA result} - \text{date of first positive ADA result} + 1)/7.$$

Duration of ADA response will be censored if:

- the last ADA assessment is positive AND patient is ongoing treatment with avelumab, or

- the last ADA assessment is positive AND patient discontinued treatment with avelumab AND the last planned ADA assessment (day 30 follow-up visit) is after the cut-off date.

Time to nAb response and duration of nAb response are defined similarly based on first and last positive nAb result.

Kaplan-Meier estimates (product-limit estimates) will be presented together with a summary of associated statistics including the median ADA response time with 2-sided 95% CIs. ADA response rates at different timepoints will be estimated with corresponding 2-sided 95% CIs. The CIs for the median will be calculated according to [Brookmeyer and Crowley \(1982\)](#) and the CIs for the survival function estimates will be derived using the log-log transformation according to [Kalbfleisch and Prentice \(2011\)](#) (confotype=loglog default option in SAS Proc LIFETEST) with back transformation to a CI on the untransformed scale. The estimate of the standard error will be computed using Greenwood's formula.

Duration of ADA response will be displayed graphically and analyzed using Kaplan-Meier methodology. If the number of patients with ADA response is small, the Kaplan-Meier method may not provide reliable estimates. In this case, only descriptive statistics or listings will be provided.

As data permit, the analyses described above will be repeated for patients with treatment-induced nAb.

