2. INTRODUCTION

This SAP provides the detailed methodology for summary and statistical analyses of the data collected in study B9991024. This document may modify the plans outlined in the protocol; however, any major modifications of the primary endpoint definition or its analysis will also be reflected in a protocol amendment.

Statistical analyses will be performed using cleaned eCRF data as well as non-CRF data (ie, pharmacokinetics/pharmacodynamics and tumor assessment results by the Blinded Independent Central Review (BICR)). The primary analysis will include all data up to a clinical cut-off date corresponding to 18 months (78 weeks) after the last patient is treated. The final analysis of the data will be performed after last patient last visit (LPLV).

Additional analyses of the data may be performed for publication or regulatory reporting purposes.

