6.2.5.2. ADA Titer

For patients who are ADA ever positive, the maximum observed ADA titer for a patient will be summarized, overall and by ADA subcategories (baseline ADA positive, treatment-boosted ADA, treatment-induced ADA, transient ADA response, persistent ADA response) of patients having each discrete maximum titer value will be tabulated. The denominator to calculate the percentages will be the total number of patients in the associated ADA subcategory.

For patients with treatment-induced ADA, a cross tabulation of duration of ADA response and maximum ADA titer will be provided. The following categories for duration of ADA response will be used: ≤ 1 , >1 to ≤ 3 , >3 to ≤ 5 , >5 to ≤ 7 , >7 to ≤ 13 , >13 to ≤ 16 , >16 to ≤ 25 , >25 weeks. In this categorization, the censoring in duration of ADA response is ignored.

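### Duration of ADA response counts patients still ADA-positive at the day-30 sample as ended responses, and one Table 10 clause uses an ADA result to define nAb status

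*SAP*

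**What the plan says.** SAP 6.2.5.1 takes patients with treatment-induced ADA, computes the number of weeks from first to last positive result, and presents a Kaplan-Meier curve with a median and confidence interval. It censors in two cases only, both with a positive last result. In the first, the patient is still on avelumab. In the second, "the last ADA assessment is positive AND patient discontinued treatment with avelumab AND the last planned ADA assessment (day 30 follow-up visit) is after" data cut-off. Duration of nAb response is defined in the same way. If responders are few, Kaplan-Meier is dropped: "In this case, only descriptive statistics or listings will be provided".

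The sample 30 days after the end of avelumab is the last one planned (Protocol 7.3; SAP 6.2.5). Table 9 in SAP 6.2.5 classes a treatment-induced response as persistent if its positives span at least 16 weeks "or a positive ADA result at the last assessment". SAP 6.2.5.2 cross-tabulates duration against maximum titer and states: "In this categorization, the censoring in duration of ADA response is ignored". The primary analysis uses a "clinical cut-off date corresponding to 18 months (78 weeks) after the last patient is treated" (SAP 2).

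Table 10 calls a nAb response treatment-induced if nAb was not positive before treatment and the following holds: "at least one positive post-baseline nAb result; or if patient does not have a baseline sample, the patient has at least one positive past-baseline ADA" finding. SAP 6.2.5.3 then compares "nAb: treatment-induced nAb versus nAb never-positive or baseline nAb positive". All nAb analyses are conditional: "As of the finalization of this SAP, the nAb assay is not yet available".

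**The concern.** A positive last result shows that the response lasted at least that long. It does not show when the response ended. The two censoring conditions accept this for patients on avelumab and for those whose day-30 visit lies beyond the cut-off. They leave out the patient who has stopped avelumab, reached day 30 by the cut-off and is still positive. The SAP does not use the word event for this patient, but anyone not censored in a Kaplan-Meier analysis is an event. The same gap covers a patient who stops avelumab with a positive last result and misses a day-30 visit that was due by the cut-off.

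Table 9 calls the same patient persistent. SAP 6.2.1.4 handles tumor response differently: a responder with no observed progression or death is censored at the last adequate assessment, whatever the treatment status. No reason is given for treating ADA otherwise.

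Immunogenicity is a secondary objective, and Protocol 9.3.1.2 undertakes to describe duration of ADA response if the data allow. The Table 10 clause raises a separate question: whether a patient can be given a nAb category without any positive nAb result.

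**Working it through.** **1. Cases with a positive last result**

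| Status | SAP 6.2.5.1 |
|---|---|
| On avelumab | Censored |
| Off avelumab, day 30 after cut-off | Censored |
| Off avelumab, day 30 on or before cut-off | Event |

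Once every patient is off avelumab and past day 30, as expected at the final analysis, no duration is censored. The curve is then only the distribution of observed spans.

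**2. Two worked patients**

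Formula: (last positive − first positive + 1)/7.

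- First positive 42 days after first dose, last dose at day 168, still positive at day 168 + 30 = 198: (198 − 42 + 1)/7 = 22.4 weeks, an event.
- First positive at the day-30 sample itself: (0 + 1)/7 = 0.14 weeks, an event, yet persistent in Table 9.

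**3. Five-patient illustration (assumed data)**

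All are off avelumab with day 30 before the cut-off. Two reverted to negative (2.1 and 8.1 weeks) and three were still positive (6.1, 12.1 and 20.1 weeks).

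- SAP rule: the curve falls 0.8, 0.6, 0.4, 0.2, 0. The median is 8.1 weeks.
- Censoring the three: 4/5 = 0.8 at 2.1 weeks, then 0.8 × 2/3 = 0.533 at 8.1 weeks. The median is not reached.

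At 6.1 weeks the gap is 0.8 − 0.6 = 0.2, which is 1/n for n = 5. In general, one miscounted patient lowers the curve at that time by at least 1/n. With an assumed ADA incidence of 10% to 50%, 20 patients give 2 to 10 responders, so the drop is 20 points with 5 responders and 10 points with 10.

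**4. Size under assumptions**

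The documents state no ADA duration, so there is no planned figure to reproduce. The simulation used 8,000 patients per scenario and sampling at days 14, 28, 42, 70 and 98, then every 56 days on avelumab, plus last dose + 30. Treatment length and persistence were exponential, ADA onset was uniform over 90 days, and the cut-off was 78 weeks after each first dose. Entries are Kaplan-Meier medians in weeks, SAP rule vs corrected, with the share of responders counted as events while still positive.

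| Median persistence | Median treatment 12 wk | 24 wk | 52 wk |
|---|---|---|---|
| 16 wk | 4.4 vs 16.1 (60%) | 8.1 vs 16.1 (42%) | 10.1 vs 12.1 (25%) |
| 52 wk | 8.4 vs 66.1 (82%) | 14.4 vs 56.1 (66%) | 24.1 vs 52.1 (44%) |
| Never clears | 10.4 vs not reached (98%) | 22.4 vs not reached (88%) | 50.4 vs not reached (61%) |

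The 66.1 rests on few patients at risk. In repeat runs it ranged from about 60 weeks to not reached, so it should not be used. Other corrected medians can shift by one sampling interval between runs. At the final analysis the shares are 60/42/25%, 82/70/51% and 100/100/100%.

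A second simulation, with mean persistence 8 to 104 weeks and mean treatment 16 or 32 weeks, compared both rules with the truth at 16 weeks. The proportion still ADA-positive was 0.04 to 0.52 under the SAP rule and 0.14 to 0.87 after correction, against true values of 0.135 to 0.857.

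**5. Table 10**

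Take a patient with no baseline sample who is ADA-positive after baseline and never nAb-positive. The no-baseline clause makes this patient treatment-induced nAb. The first row of Table 10 makes the same patient nAb never-positive. The patient falls on both sides of the SAP 6.2.5.3 comparison and has no first positive nAb date for the formulas in 6.2.5.1.

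**The case against.** The strongest reply is that duration is defined as the observed span and that censoring only marks incomplete planned sampling. Once the day-30 sample is in, the span is complete. Read that way the rule is coherent, and there is bias only if the target is how long ADA truly lasts. But with complete observed spans neither Kaplan-Meier nor censoring would be needed, and reaching day 30 says nothing about clearance in a patient who is still positive.

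It can also be said that persistent in Table 9 is a category, since it includes long spans that later turned negative. That is fair. Even so, a still-positive patient cannot be transient in Table 9, while 6.2.5.1 treats that patient's response as finished.

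Several points on materiality stand. There is no hypothesis test or decision rule. Few responders would trigger the descriptive fallback, so with 2 responders there would probably be no curve to distort. SAP 6.2.5.3 already lists first and last positive dates and avelumab stop dates for ADA ever-positive patients. The cross-tabulation in 6.2.5.2 openly ignores censoring. The corrected median would often be not reached: with 2 to 10 responders, 24-week treatment and 52-week persistence, this happened in about half of simulated trials. That would be the honest result in those trials. Finding a lower median in all nine scenarios adds little, because the direction follows from the estimator.

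**Conclusion.** The concern holds on both counts. For the true duration of ADA positivity, the rule in SAP 6.2.5.1 can only lower the Kaplan-Meier curve or leave it unchanged. The size cannot be taken from the documents. Over the assumed ranges it runs from about 2 weeks on the median (12.1 − 10.1 = 2.0) to a finite median where the corrected one is not reached. In the descriptive fallback the same spans would read as completed durations unless flagged.

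The Table 10 clause looks like a carry-over from Table 9. It needs a missing baseline sample, although a Cycle 1 pre-dose sample is planned, and it matters only if nAb data become available. It does not affect the nAb ever-positive, transient or persistent categories.

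The importance is minor to moderate. The primary safety endpoint is untouched, but the rule is wrong as written and should be corrected.

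**What to change.** - In SAP 6.2.5.1, censor duration at the last positive sample whenever the last valid ADA (or nAb) result is positive, regardless of treatment status or cut-off.
- Flag these durations as censored in any listing or descriptive summary that replaces Kaplan-Meier.
- In Table 10, make the no-baseline clause require a positive post-baseline nAb result.

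The cost is one SAP sentence, one listing flag and one word in a table, with no new data. The change does not remove a smaller understatement in patients who revert to negative, whose duration still ends at the last positive sample.
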